Exclusion Criteria	
 1. Any of the previous facial treatments: 
 a. Any facial filler in the past 2 years b. Prior injection of permanent facial implant 2. Have any skin pathology or condition that could interfere with the evaluation of the face. 3. Be unable to communicate or cooperate with the Investigator due to a language barrier (non-English speaking), poor mental development, or impaired cerebral function. 4. Have evidence of alcohol or drug abuse (Investigator opinion), or history of poor cooperation, non-compliance with medical treatment, or unreliability. 5. Have used an investigation device, biologic or drug in the past 30 days, or be currently participating in an experimental drug, biologic or device trial. 6. Have a condition or be in a situation that, in the Investigator's opinion, may put the subject at significant risk, may confound the study results, or may interfere significantly with the subject's participation in the study. 7. Be an employee (or a relative of an employee) of the Investigator, Sponsor or representative of the Sponsor.
Study Measurements	Subject self-reported quality of life scale
Study Procedures and Assessment Schedule	Eligible subjects will be given a self report questionnaire to complete 1 month after their second or third injection while in the physician's office. A subset of subjects will have baseline and post injection photographs taken.
Statistical Methods	Data will be summarized using descriptive statistics.

1. Background and Rationale

Facial volume loss can substantially impact both self perception of the affected individual and their social/professional interactions and opportunities. Persons who are perceived as more youthful and attractive are rated as nicer, more energetic, healthier, and more likely to be productive than those perceived to be older and unattractive.

The observed facial changes that result from underlying volume loss often produce an older and less attractive appearance. Loss of facial volume often produces a sad, sunken, deflated, dull, tired, and lackluster appearance. These changes can be interpreted as evidence of aging and loss. In addition, some may consciously or subconsciously see them as harbingers of progressive deterioration and decline. Filler correction of localized areas of facial volume loss has been demonstrated to affect positive changes in emotional and functional status by patient self report measures.

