2. Current Clinical Study

A concern among some clinicians is the “delayed gratification” aspect of poly L-Lactic Acid. While its efficacy, safety, and duration of benefit are well supported by the literature, it is unique as a biostimulator leading to the gradual onset of tissue augmentation over several months. Many clinicians wonder whether patients will objectively “remember” their baseline appearance and thus be satisfied with their ultimate cosmetic outcome.

The goal of this study is to assess both the short term and longer term (3 months post first injection and 6 months post first injection) satisfaction with facial volume restoration with poly L-Lactic Acid.

Specifically, a patient self report questionnaire, previously utilized in several facial filler studies, will be completed by study participants at 3 months and six months after their initial facial injections to assess the emotional and functional effects produced by pan facial treatment with Poly-L-Lactic Acid. The obtained data will hopefully further enhance our appreciation and understanding of the benefits of facial volume restoration. Insight will hopefully be provided into the benefits of gradual onset of volumization with prolonged duration of improvement.

Buttressing and clarifying the data on the emotional and functional benefits of facial volume restoration can further “legitimize” treatment with poly L-Lactic Acid as an effective and meaningful medical procedure. Dissemination of data substantiating that volume restoration is more than simply a vanity or cosmetic intervention can serve as a compelling “recruitment tool” for the growing number of “maturing persons” struggling with the deflation and lackluster appearance that accompany the volume loss associated with aging, medications, stress, and illness.

3. Objectives

Objective 1: To assess the emotional and functional improvement produced by pan facial improvement with Poly-L-Lactic Acid

Objective 2: To assess to stability of these affects after treatment

Objective 3: To further substantiate the legitimacy and value of facial volume restoration.

4. Study Design

This is a multi-center study utilizing 2 centers (Yardley Dermatology Associates, [name] and Spokane Dermatology-[name] Aesthetics, [name]. Subjects will be recruited from private practice dermatology offices. Eligible patients must meet the inclusion and exclusion criteria as stated below.

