5.3 Exclusion Criteria

1. Any of the previous facial treatments:
 - c. Any facial filler in the past 2 years
 - d. Prior injection of permanent facial implant
2. Have any skin pathology or condition that could interfere with the evaluation of the face.
3. Be unable to communicate or cooperate with the Investigator due to a language barrier (non-English speaking), poor mental development, or impaired cerebral function.
4. Have evidence of alcohol or drug abuse (Investigator opinion), or history of poor cooperation, non-compliance with medical treatment, or unreliability.
5. Have used an investigational device, biologic or drug in the past 30 days, or be currently participating in an experimental drug, biologic or device trial.
6. Have a condition or be in a situation that, in the Investigator's opinion, may put the subject at significant risk, may confound the study results, or may interfere significantly with the subject's participation in the study.
7. Be an employee (or a relative of an employee) of the Investigator, Sponsor or representative of the Sponsor.

6. Enrollment

Subjects will have the study explained and will be asked about their willingness to participate, including their willingness to sign an informed consent and a photography release form. To comply with Health Insurance Portability and Accountability Act (HIPAA) requirements, a separate authorization for disclosure or use of protected health information will be signed. After full consent, subjects will be considered enrolled into the study.

7. Informed Consent and Subject Privacy

The purpose and procedures to study participation will be discussed with each potential subject. Prior to any study-related procedures subjects must give their written informed consent. The subject must also give Authorization for Use and Release of Health and Research Study Information (HIPAA), authorization to take identifying clinical photographs for scientific and regulatory use and other written documentation required by local regulations and/or the reviewing IRB prior to any study-related procedures.

8. Study Assessments

Prior to enrollment of any study subjects, the Investigators will be trained in the use of the assessment scale. Subjects will receive training on how to complete the Volume Restoration Quality of Life Scale..

The Sponsor will prepare written procedures on how to perform digital imaging in a standardized fashion.

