8.3 Photography

Photographs for the study may be taken only at an investigators site as designated by the sponsor. Written training regarding study related photography will be provided during site initiation visits (where applicable).

9. Schedule of Study Activities

Subjects must meet all screening criteria as assessed by subject interview and through examination of facial volume loss. Please refer to the following schedule for additional details:

1. Discuss with each subject his/her willingness to participate in the study and obtain Informed Consent/HIPAA.
2. Inclusion/Exclusion Criteria
3. Document Subject Demographic Information
4. Subject Photography
 - a. To be conducted at baseline prior to first injection and 3 month and 6 month post initial injection. Photography instructions to be provided in a separate study document.
5. Facial volume loss assessment by Investigator and subject
 - a. Investigator/Subject Facial Volume Loss Global Assessment
6. Subjects will receive 1 vial of poly-L-lactic acid reconstituted in the usual sterile fashion with 7cc of sterile water and 2cc of Lidocaine without epinephrine. The contents of the vial will be injected as deemed appropriate by the certified injector and agreed upon by the study subject.
7. Approximately 4-6 weeks later, a second vial will be reconstituted as above and injected according to the above parameters.
8. Approximately 4-6 weeks later (8-12 weeks after the first injections), subjects will be evaluated and a decision jointly made with the injector regarding whether a third vial is desired and appropriate.
9. Injection sites will be prepared in the usual sterile fashion and sites will have Lidocaine topical application 30-90 minutes before the procedure.
10. All subjects will receive full informed consent and will have time for any questions before procedures are initiated.
11. Explicit post procedure instructions will be provided as per usual protocol.
12. Subjects will be instructed to contact the study site immediately with any concerns after each injection session.
13. QOL and Self-Esteem measures by subject
 - a. To be completed 3months and 6 months post initial injection.

10. Early Discontinuation/Withdrawal

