APPENDIX 1: Facial Volume Restoration Outcome Questionnaire

Site # _____ Subject # _____

Date: _____

Treatment visit 1 date: _____

Sex: Female Male

Treatment visit 2 date: _____

Age: 35-45 45-60 60-75

Treatment visit 3 date: _____

City/Country of residence: _____

Number of Poly-L-Lactic Acid treatments: _____

Please circle the number that best describes how you feel. Circling the number one suggests that you believe that the description on the left hand column best describes how you feel. Circling the number 7 suggests that you believe that the description on the right hand column best describes how you feel. Circling number 4 suggests that you feel that there has been no change. Please be honest.

Since my Poly-L-Lactic Acid injection (s), I find that I am in general...

1. Less anxious	1 2 3 4 5 6 7	More anxious
2. More optimistic	1 2 3 4 5 6 7	Less Optimistic
3. More energetic	1 2 3 4 5 6 7	Less energetic
4. Eating more healthy food	1 2 3 4 5 6 7	Eating less healthy food
5. Happier	1 2 3 4 5 6 7	Sadder
6. Exercising more	1 2 3 4 5 6 7	Exercising less
7. Less irritable	1 2 3 4 5 6 7	More irritable
8. More amorous	1 2 3 4 5 6 7	Less amorous
9. More social	1 2 3 4 5 6 7	Less social
10. More productive	1 2 3 4 5 6 7	Less productive
11. More focused	1 2 3 4 5 6 7	Less focused
12. Less tired	1 2 3 4 5 6 7	More tired
13. Less angry	1 2 3 4 5 6 7	More angry
14. More confident	1 2 3 4 5 6 7	Less confident
15. More sexually confident	1 2 3 4 5 6 7	Less sexually confident
16. More assertive	1 2 3 4 5 6 7	Less assertive
17. Less argumentative	1 2 3 4 5 6 7	More argumentative
18. More comfortable with others	1 2 3 4 5 6 7	Less comfortable with others
19. More likely to go out	1 2 3 4 5 6 7	Less likely to go out
20. More involved in community activities	1 2 3 4 5 6 7	Less involved in community activities
21. Doing better at work/school	1 2 3 4 5 6 7	Doing worse at work/school
22. More in control	1 2 3 4 5 6 7	Less in control
23. Taking more medications	1 2 3 4 5 6 7	Taking less medications
24. Less depressed	1 2 3 4 5 6 7	More depressed
25. Seen by others as less stressed	1 2 3 4 5 6 7	Seen by others as more stressed
26. Feeling more attractive	1 2 3 4 5 6 7	Feeling less attractive

27. More relaxed	1 2 3 4 5 6 7	Less relaxed
28. Happier when looking in mirror	1 2 3 4 5 6 7	Less happy looking in mirror
29. Using less cosmetics to hide defects	1 2 3 4 5 6 7	Using more cosmetic to hide defects

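### The Appendix 1 stem ties change to the injection(s) but names no single pre-treatment comparator, so a 4 is ambiguous and the 3- versus 6-month stability assessment is at risk in either direction

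*Combined protocol and SAP*

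**What the plan says.** **The form.** The 35 items in Appendix 1 share the stem "Since my Poly-L-Lactic Acid injection (s), I find that I am in general". Responses run from 1 to 7, and the instructions explain the midpoint: "Circling number 4 suggests that you feel that there has been no change". They do not say from what. The header has spaces for three treatment visit dates and the number of treatments, but no item refers to any of those dates.

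**The treatment course.** Section 9 describes a first vial, then "Approximately 4-6 weeks later, a second vial will be reconstituted as above", and then a visit about a possible third: "Approximately 4-6 weeks later (8-12 weeks after the first injections), subjects will be evaluated and a decision jointly made with the injector".

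**When the form is completed.** Section 9, item 13 says of the quality-of-life and self-esteem measures: "To be completed 3months and 6 months post initial injection". Section 2 gives the same two times. Neither section schedules the form before treatment. The synopsis differs: subjects are to "complete 1 month after their second or third injection while in the physician's office".

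**What the form must support.** Section 3 includes "Objective 2: To assess to stability of these affects after treatment". Section 13 plans descriptive summaries only, with no rule for comparing the two visits.

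**Training.** Section 8 states: "Subjects will receive training on how to complete the Volume Restoration Quality of Life Scale". The content of that training is not given.

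**The concern.** Each answer is a self-rated change, so it has meaning only relative to a starting state. With a single treatment session, the word *since* would leave little doubt about that state. With two or three sessions, a subject can reasonably think of the start of the course or of the latest injection.

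Objective 2 concerns stability, and Section 2 sets short-term against longer-term satisfaction. Both imply setting the 3-month answers beside the 6-month answers. That works only if the two sets of ratings share a comparator. If they do not, a difference between visits may reflect a change of comparator and not a change in the subject, and equal scores may hide a real change.

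The problem cannot be repaired afterwards. The form records treatment dates but not which state the subject had in mind, and there is no pre-treatment form to check against. Section 2 itself reports clinicians' doubt about whether patients recall their starting appearance when the effect builds over months. In such a study the starting state should be named on the form.

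**Working it through.** The plan gives no figure on this point to reproduce. The check has two parts: how far apart the candidate comparators lie in time, and in which direction a mixed comparator would move the comparison between visits.

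**1. Timing**

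Inputs from Section 9: second injection 4-6 weeks after the first; decision visit for a third at 8-12 weeks; forms at 3 and 6 months. Assumption: a third vial, if given, is injected at about the decision visit.

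Conversion: 3 months = 3 × (365.25/12)/7 = 13.0 weeks; 6 months = 26.1 weeks.

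| Time since | 3-month form | 6-month form |
|---|---|---|
| First injection | 13.0 weeks | 26.1 weeks |
| Second injection (week 4-6) | 13.0 − 6 to 13.0 − 4 = about 7-9 weeks | 26.1 − 6 to 26.1 − 4 = about 20-22 weeks |
| Third injection (week 8-12) | 13.0 − 12 to 13.0 − 8 = about 1-5 weeks | 26.1 − 12 to 26.1 − 8 = about 14-18 weeks |

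The stem can thus point to dates up to 12 weeks apart. For a subject with three injections, judging against the last one covers only 1-5 weeks at the first form.

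**2. Direction**

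Take an item on which lower scores mean benefit. Let *s* (below 4) be the score against the pre-treatment state, truly stable across both visits. Let *p3* and *p6* be the shares of subjects using another comparator at 3 and 6 months, and *m3* and *m6* the mean scores those subjects give. The expected means are:

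- 3 months: (1 − p3)·s + p3·m3
- 6 months: (1 − p6)·s + p6·m6

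The expected difference, 6 months minus 3 months, is

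D = p6·(m6 − s) − p3·(m3 − s).

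The true difference is zero. Three cases follow:

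- **Everyone uses the pre-treatment state** (p3 = p6 = 0): D = 0, no distortion.
- **Some shift only at 6 months and circle 4** (p3 = 0, m6 = 4): D = p6·(4 − s), which is positive. A stable benefit looks partly lost.
- **The same share judges against the last injection at both visits** (p3 = p6 = p): D = p·(m6 − m3). Section 2 describes onset as gradual over several months. Such subjects may report little change 1-5 weeks after a third injection (m3 near 4) and more at 14-18 weeks (m6 below m3). D is then negative, and a stable benefit looks like a gain.

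The sign depends on quantities the documents do not give. Items 23 (medications) and 32 (alcohol) are printed with the less favourable pole on the left, so for them the signs reverse.

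**The case against.** The strongest reply is that the stem does fix a reference. It ties change to treatment, its optional plural covers the whole course, and the ordinary reading is after versus before. The header above it lists all the treatment visits, which supports that reading. On it, a maintained benefit still scores on the improved side at 6 months. This stands, and it limits the point: the stem is anchored to treatment, but it does not name the state before the first injection.

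A reader might infer more: that the 6-month form will show a false decline, because subjects compare with the 3-month form or the last injection and circle 4. The documents do not support that. Nothing in Appendix 1 mentions an earlier form, and a last-injection reading can produce a false gain as easily as a false loss. Nor can a percentage loss be attached. If a share p shifts only at 6 months and circles 4, the apparent loss as a fraction of benefit is p·(4 − s)/(4 − s) = p, whatever *s* is. The result only repeats the assumed share.

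Two mitigations are partial. The self-esteem scale in Appendix 3, due at the same two times, asks about current status and does not depend on this stem, but it covers self-esteem only. Training is planned, but the documents do not show that it covers the comparator.

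It is also fair to say that Section 13 specifies no comparison between the visits. The comparison is inferred from Objective 2 and the aim in Section 2. It exists only under the two-visit schedule in the body, not under the single completion in the synopsis.

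**Conclusion.** The point holds as an under-specified comparator. With two or three injections over up to about 12 weeks and no baseline form, a 4 does not distinguish no benefit against the pre-treatment state from no further change since a later injection. If the comparator differs between subjects or visits, the stability assessment can be biased in either direction, and the planned descriptive analysis can neither detect nor correct it.

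No size can be given. The distortion is zero if all subjects read the stem as after versus before the whole course, and the documents do not show how many would read it otherwise. It is a risk to Objective 2, not evidence of a decline that did not occur. The conclusion assumes the 3- and 6-month schedule in Sections 2 and 9. Under the synopsis timing, the ambiguity of a 4 remains but there is no second visit to compare. A correction is justified because it costs little and cannot be made once forms have been completed.

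**What to change.** Leave the 35 items and the 1-7 scale unchanged. Add one line above item 1, identical at both visits: *Compare how you are now with how you were before your first injection.* Say the same in the subject training under Section 8, and record in the protocol that the training covers it.

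The cost is one printed line and one training sentence. The downside is a minor difference from the instruction page used in the earlier filler studies that Section 2 mentions; the items and scoring are not affected.

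The line gives both visits the same reference but does not remove the reliance on memory. Without a baseline form, subjects must still recall a state up to six months past, and the report should state this as a limitation.

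Separately, the questionnaire timing in the synopsis and that in Sections 2 and 9 must be reconciled.

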APPENDIX 2: Investigator Global Assessment (IGA) of Facial Volume Loss

Grade	Description
0	No visible volume loss
1	Mild volume loss.
2	Moderate volume loss
3	Severe volume loss
4	Very severe volume loss

APPENDIX 3: Rosenberg Self-Esteem Scale

Rosenberg Self-Esteem Scale

Circle one response for each of the following ten items.

	Strongly		Strongly	
	Agree	Agree	Disagree	Disagree
1. I feel that I am a person of worth, at least on an equal basis with others.	1	2	3	4
2. I feel that I have a number of good qualities.	1	2	3	4
3. All in all, I am inclined to feel that I am a failure.	1	2	3	4
4. I am able to do things as well as most other people.	1	2	3	4
5. I feel I do not have much to be proud of.	1	2	3	4
6. I take a positive attitude toward myself.	1	2	3	4
7. On the whole, I am satisfied with myself.	1	2	3	4
8. I wish I could have more respect for myself.	1	2	3	4
9. I certainly feel useless at times.	1	2	3	4
10. At times, I think I am no good at all.	1	2	3	4

Source: Morris Rosenberg's "Self-Esteem Scale" from pp-325-327 of *Society and Adolescent Self-Identity* 1989 by Morris Rosenberg, Wesleyan University Press.
